Appendix V: The CONSORT diagram of the cluster randomized controlled trial

*Baseline & Outcome Assessments: Fatigue, Physical Endurance, Exercise Self-efficacy Fried Frailty Index, Habitual Physical Activity, Depressive Mood, Exercise Adherence (only for the EXER & COMB groups);

[^]HAPA: Health Action Process Approach

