The changes in the mean fatigue scores were -0.58, -5.16, and -2.66 for the control, EXER, and COMB groups respectively, from pre-test to immediately post-intervention in the pilot study. The Cohen's d effect sizes for the EXER and COMB groups were 0.51 and 0.23, respectively; whereas the overall effect size was 0.21. As no similar cluster-RCT has been reported in the literature and the cause of general fatigue is heterogeneous, we assumed that an intra-correlation coefficient would be low (0.01) within each cluster (43). Based on an effect size of 0.21 in the pilot study, and four clusters (community centres) per group with an intraclass correlation of 0.01, a significance level (α) of 0.05, and a power ($1-\beta$) of 0.8 for a two-sided test, the sample size was calculated to be 76 participants per group according to NCSS PASS 14. For a long-term follow-up of 12 months, 285 participants (95 per group) will be recruited after considering an attrition rate of 20%. Using computer-generated random numbers, a biostatistician not affiliated with this study will randomize the centres into either: control, EXER, or COMB. The randomization will be stratified based on the size of the centres. Small-medium centres will be defined as those with < 800 ($n=9$) clients, whereas those with > 800 clients will be defined as large ($n=3$). The number of participants recruited in each centre will be in proportion to the size of the centre (i.e., the total number of clients). We estimate that about 25-50% (4, 16, 44) of the 8,710 members of these centres will be eligible to participate. To avoid selection biases, the allocation to the study groups will be concealed from the researchers until the recruitment of the sample and measurement of the baseline have been completed (please refer to the item 13 in this application for details of the collaborators).

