Participants will be assessed on a variety of outcomes (described below) at week 8 (T1 at mid-term programme), 1 week (T2 immediate effect), 6 and 12 months after the programme (T3 and T4), which will be compared with the baseline assessment (T0). All assessments will be carried out by a part-time RA, regarded as an independent assessor, who will be blinded to the group assignments.

Socio-demographic data: The following data will be collected: 1) age, gender, marital status,

exercise habits, living conditions, and level of education, 2) the participants' health-related information, including cognitive status and medications. Additionally, their levels of comorbidity will be assessed using the Chinese version of the Charlson comorbidity index (C-CCI). The C-CCI score is the sum of the comorbidity and age scores, in which scores of 0, 1-2, 3-4, and > 5 represent the comorbidity level as none, low, medium, and high, respectively⁵⁰. The health services utilization of the parents in the past 12 months and during the study period, such as the number, duration, and causes of hospital admissions and scheduled/non-scheduled clinical visits, will be collected during each measurement time point and will be treated as a co-variate if needed.

Primary outcome measurement: Fatigue will be assessed using the 20-item Chinese Multidimensional Fatigue Inventory (CMFI-20)⁽⁵¹⁾. This scale was validated among 385 local cancer patients. A factor analysis revealed that it contains three factors (namely, physical, mental, and spiritual) with a factor loading ranging from 0.52 to 0.75. The Cronbach's α was between 0.7 and 0.8 for three domains and the total of the CMFI-20 score. It supports the view that the CMFI-20 is a reliable and valid instrument.

Secondary outcome measurements

Physical Endurance will be evaluated using different physical tests. First, the participants' lower-limb and upper-limb strength will be assessed using a 30-second chair stand test⁽⁵²⁾ and a handheld Jamar Hydraulic Hand Dynamometer⁽⁵³⁾, respectively. Their mobility and overall physical endurance will be assessed through the TUG test and by their gait speed (6-m walk).

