Procedures: (*Appendix IV*: Detailed Ethical Considerations; *Appendix V*: CONSORT diagram of the Cluster RCT) Ethical and access approval will be obtained from the Ethics Review Committee of The University and study venues, respectively. Potential participants will be referred to the research team by the collaborators. An RA will screen all potential participants for their eligibility to participate in this study. Written informed consent will then be obtained from all of the participants, to whom all aspects of the study will be explained and questions answered. They will then be interviewed to obtain their health-socio-demographic data, and baseline assessment. After that, the twelve community centres will be randomized to either the control, EXER, or COBM group. Participants from each centre will be placed into their centre's corresponding group to avoid 'contamination' effects across participants. At the mid-term programme, 1 week, 6 months, and 12 months post-intervention, an independent assessor who is blinded to the group allocations will assess the participants' outcomes, which will be compared with the baseline assessment. Focus group interviews will be conducted by the trained RA after the first post-test 1 (one-week post-intervention). Purposive samples of 30 participants from the COMB group will be selected to take part in one interview (4-6 per group). They will be asked to comment on their experiences and (dis)satisfaction regarding the programme, perceptions of its positive/negative aspects, concerns and difficulties in participating and adhering to the programme, and ways of improving the intervention. A semi-structured interview guide will be developed for these interviews, which will be conducted in Cantonese, and all interviews will be audio-recorded for content analysis. Examples of interview questions include: "What are your opinions and comments on your participation in the programme?" and "What are your changes and / or difficulties in adherence to the exercise regimen during and after the 16-week programme?"

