SPSS version 23.0 will be used to analyse the data. An intention-to-treat analysis will be adopted. Descriptive statistics will be generated for the demographic data. Normality assumptions for the variables will be checked. The baseline characteristics of the participants in the three groups will be compared using ANOVA for the continuous variables, a chi-square test for the categorical variables, and the Kruskal-Wallis test for the ordinal variables. Mixed-effects modelling will be used to measure changes in the outcome assessments across the mid-term programme (at week 8) and the three post-tests (1 week, 6 months, and 12 months after the intervention) among the three groups, followed by the Helmert contrasts test (if any results are found to be significant)(60). Another mixed-effects modelling approach will be used to measure the participants' attendance rate in the weekly exercise sessions and their adherence to the home exercise during the programme and the follow-up period between the EXER and the COMB groups. Any pre-test outcome scores, demographic information, data on health conditions, comorbidity index, health service utilization, dosages of exercise recommended by the physiotherapist, and participation in other exercise programmes during the study period, indicating significant differences between groups, will be treated as co-variates as needed. Multiple imputations will be adopted to manage missing data. A p-value of < 0.05 will be considered statistically significant. Content analysis will be used to analyse the interview data⁶¹. All audio-taped interviews will be transcribed into Chinese by the RA and the transcriptions will be checked for accuracy by the PI using QSR NVivo 11. The revised transcripts will be coded independently by two (Chinese-speaking) Co-Is. The research team will then discuss the identified codes and come to an agreement on them, grouping them into main (sub)categories with the support of verbatim data. The (sub)categories will then be condensed and/or re-organized when deemed necessary. The research team will examine them for consistency, reach a consensus about their meaning and structure, and devise a list of finalized categories. A set of (sub)categories with supporting verbatim data will finally be generated to identify the major strengths and limitations of the combined intervention to come up with improvements for its future use.

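### The blinded assessor is given all assessments, yet exercise adherence is listed for the two exercise arms only and no one else is named to collect it

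*Protocol*

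**What the plan says.** The design is described as single-blinded. Under Instruments and Measures the Protocol opens with "Participants will be assessed on a variety of outcomes (described below) at week 8" and goes on to the three later time points. It then says: "All assessments will be carried out by a part-time RA, regarded as an independent assessor, who will be blinded to the group assignments". The Procedures section repeats, for the mid-term visit and the three post-tests, that "an independent assessor who is blinded to the group allocations will assess" the outcomes.

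The note under the CONSORT diagram in Appendix V lists the baseline and outcome assessments. After six domains common to all arms it adds "Exercise Adherence (only for the EXER & COMB groups".

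The SAP plans a second mixed-effects model for attendance at the weekly sessions and for "their adherence to the home exercise during the programme and the follow-up period between the EXER and the COMB groups".

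On allocation, the Procedures section places randomization after the baseline interview: "After that, the twelve community centres will be randomized to either the control, EXER, or COBM group". The sample size section gives "four clusters (community centres) per group".

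**The concern.** If the person who must not know the allocation also administers an item that exists in only two of three arms, the item itself carries the allocation. Its presence says exercise, its absence says control, and a participant's answer about prescribed home exercise says the same. With whole centres allocated, this knowledge extends to every participant at that centre and to every later visit.

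The outcome assessor is the only role that the documents describe as blinded during follow-up, so this is the trial's one stated protection against biased outcome assessment. Chair stand, grip strength, TUG and gait speed all depend on effort and on how the test is run, and grip and walking speed also feed the frailty index. Both comparisons of an exercise arm with control would be exposed.

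**Working it through.** The plan gives no figure to reproduce, so the check is a comparison of its statements, with simple counts at the end.

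1. **Is adherence within the assessor's task?** Instruments and Measures assigns all assessments to the blinded assistant. Appendix V calls adherence an assessment and sets it in the same list as fatigue, endurance, self-efficacy, frailty, activity and mood, all of which that assistant measures. Taken literally, adherence is included.

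2. **Could a class register supply it instead?** Only in part. Centre classes run in weeks 4 to 16. The SAP also needs home-exercise adherence, and needs it in follow-up, which extends to 12 months after the programme. That information must come from the participant.

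3. **Is it routed to anyone else?** The measures section has no entry for adherence: no instrument, source or collector. The Protocol does separate roles elsewhere, since the health talks go to another research assistant who takes no part in other procedures. It makes no such statement for adherence, and does not place the item after the other outcomes or give control participants a matching item.

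4. **Which visits?** Centres are randomized after baseline, so an arm-specific item cannot operate at T0. The exposure is at T1 (week 8), T2 (1 week after the programme), T3 (6 months) and T4 (12 months).

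5. **What is revealed?** The item is present in EXER and COMB and absent in control. It separates control from exercise. It does not separate EXER from COMB.

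6. **How far does it reach?** With four centres and 95 planned participants per arm:
   - centres with the item: 2 × 4 = 8; without it: 4; total 12
   - participants with the item: 2 × 95 = 190; without it: 95; total 285
   - average recruited per centre: 285 / 12 = 23.75, about 24

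   The last figure is only an average, because recruitment is proportional to centre size. One observation at each of the 12 centres would be enough to sort the whole trial into control and exercise.

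**The case against.** The strongest reply is that the statement about all assessments follows directly on outcomes said to be described below it, and adherence is not described there. On that narrower reading the assistant's task stops at the listed measures and the sections are compatible.

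The Appendix V note also cannot be a literal battery for each visit: it covers baseline, when no arm-specific item is possible. It may simply pool the trial's measures, and the diagram it annotates is not available in the text reviewed. Other staff are plausible sources too. The instructor sees attendance, the physiotherapist's recommended dosage is recorded, and COMB participants review their compliance in the BCE and booster sessions. Finally, PASE-C asks everyone about leisure activity, so participants may disclose classes whatever is done about adherence.

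Much of this stands. A reader might infer that the two rules cannot both be followed, or that the assessment schedule is proven to break the blind. The documents do not go that far: they never say that the blinded assistant collects adherence. What the reply does not supply is any sentence assigning the item to someone else. Plausible alternative sources are not an instruction, and none of them is given the task of recording home exercise in EXER and COMB over follow-up. Disclosure through PASE-C is a reason to brief participants, not a reason to leave an arm-specific item unassigned.

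**Conclusion.** The concern holds as an unprotected route to unblinding. Read literally, the plan lets the assessor learn at T1 to T4 which centres are control; on the narrower reading this is avoidable, but nothing written prevents it. Its reach is 4 control centres set apart from 8 exercise centres, with one observation classifying a whole centre.

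The size of any resulting bias cannot be estimated. A reader might be tempted to set an assumed shift against the pilot differences from control in fatigue (5.16 − 0.58 = 4.58 for EXER, 2.66 − 0.58 = 2.08 for COMB) and quote a percentage. That would only restate the assumption, because the documents give no value for such a shift. It would also use the wrong measure: the clearest mechanism is effort and encouragement in the physical tests, whereas the pilot figures are fatigue scores. The documents do not say whether CMFI-20 is self-completed or given by interview, so exposure of the primary outcome is uncertain. The concern is greatest for chair stand, grip, TUG and gait speed.

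The EXER versus COMB comparison is not affected by this route. The conclusion rests on no unseen manual having already assigned the item to other staff.

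**What to change.** State in Instruments and Measures, in Procedures and in Appendix V that the outcome assessor neither collects nor sees adherence, attendance or prescribed-dose records. Then:

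- Take centre attendance from the exercise instructor's register.
- Have existing unblinded staff collect home adherence, in the same way in EXER and COMB, since the SAP compares those arms.
- Alternatively, ask the same neutral home-exercise question in all three arms after all other outcomes are recorded at each visit. This is the weaker route if the assessor asks it, because an answer can still inform the next visit at the same centre. The statement above would then need this one exception.
- Ask participants not to mention their sessions to the assessor.
- Keep exercise adherence in the Appendix V list, marked as not collected by the blinded assessor.

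A separate system of logs with reminders by post or telephone is best avoided: it would add contact in two arms only, whereas the Protocol matches the number and timing of health talks to the BCE sessions.

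The cost is protocol wording plus a re-routed form, or one extra question for control participants. No new staff are needed, and the planned adherence comparison is unchanged.

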SPSS version 23.0 will be used to analyse the data. An intention-to-treat analysis will be adopted. Descriptive statistics will be generated for the demographic data. Normality assumptions for the variables will be checked. The baseline characteristics of the participants in the three groups will be compared using ANOVA for the continuous variables, a chi-square test for the categorical variables, and the Kruskal-Wallis test for the ordinal variables. Mixed-effects modelling will be used to measure changes in the outcome assessments across the mid-term programme (at week 8) and the three post-tests (1 week, 6 months, and 12 months after the intervention) among the three groups, followed by the Helmert contrasts test (if any results are found to be significant)(60). Another mixed-effects modelling approach will be used to measure the participants' attendance rate in the weekly exercise sessions and their adherence to the home exercise during the programme and the follow-up period between the EXER and the COMB groups. Any pre-test outcome scores, demographic information, data on health conditions, comorbidity index, health service utilization, dosages of exercise recommended by the physiotherapist, and participation in other exercise programmes during the study period, indicating significant differences between groups, will be treated as co-variates as needed. Multiple imputations will be adopted to manage missing data. A p-value of < 0.05 will be considered statistically significant. Content analysis will be used to analyse the interview data⁶¹. All audio-taped interviews will be transcribed into Chinese by the RA and the transcriptions will be checked for accuracy by the PI using QSR NVivo 11. The revised transcripts will be coded independently by two (Chinese-speaking) Co-Is. The research team will then discuss the identified codes and come to an agreement on them, grouping them into main (sub)categories with the support of verbatim data. The (sub)categories will then be condensed and/or re-organized when deemed necessary. The research team will examine them for consistency, reach a consensus about their meaning and structure, and devise a list of finalized categories. A set of (sub)categories with supporting verbatim data will finally be generated to identify the major strengths and limitations of the combined intervention to come up with improvements for its future use.

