Aim: The aims of this study are to investigate the effects of an individualized exercise programme with and without BCE strategies for community-dwelling frail older people with general fatigue, so as to reduce their fatigue and improve their physical endurance, exercise self-efficacy, and habitual physical activity, while reducing their symptoms of frailty.

Design: A single-blinded three-arm cluster-RCT is proposed to examine the effect of a 16-week individualized exercise programme with or without BCE strategies for frail older people with general fatigue. To explore the way in which the combined intervention will be implemented (42), a focus group with 30 COMB participants (4-6 per group) will be interviewed by a trained research assistant (RA) to identify the strengths, limitations, and therapeutic components of the combined intervention from their perspectives.

Subjects and Settings: Eligibility criteria for district community health centres are those that are funded by the Hong Kong (HK) government and under the supervision of the Social and Welfare Department of HK, and thus that meet a specific set of standard regulations and criteria on environment and practices. All twelve community centres, which provide similar types of community care and social support services for community dwelling older people, have been invited by a convenience method to work as collaborators in this study. The target population of this study are community-dwelling frail older people with general fatigue with a nonspecific cause who will be recruited through the community centres.

Sample size estimation, recruitment procedures, random allocation, and allocation concealment:

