Interventions: (*Appendix II:* Overview of the combined intervention) A 16-week programme with a combination of exercise and the BCE programme (plus two booster BCE sessions will be held at 2 and 6 months after the programme) will be arranged for the COMB group. Another 16-week programme with a combination of exercise and health talks will be arranged for the EXER group, whereas participants in the control group will attend only the health talks with no other intervention. Two added health talks will be arranged at 2 and 6 months after the programme for the EXER and the control groups. To control the group and social interaction effects of the BCE programme for the COMB group, the number and timing of the health talks for the other two groups will be similar to those in the BCE sessions. All face-to-face sessions will have < 10 participants to maintain good interactions between the participants and the exercise instructor / BCE facilitator/ health talk speakers.

The behavioural change enhancement (BCE) programme in the COMB group (Appendix III: BCE programme protocol) aimed at motivating the participants to develop the intention to actively manage their fatigue; and to encourage them to gradually exceed the perceived limits of their energy and to recondition their bodies by participating in exercise according to their individual exercise regimens. The BCE programme was designed based on the HAPA model and was piloted by the PI

(14). It consists of three phases with six face-to face one-hour sessions plus two booster BCE sessions at 2 and 6 months. The first three weekly sessions will be arranged during the ‘goal initiation’ and ‘planning’ phases. The remaining three sessions and two booster sessions will be offered once per month in weeks 4, 8, and 12 during the programme; and at 2 and 6 months after the programme during the ‘action execution’ phase.

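### The only follow-up named for the outcomes is an unspecified Helmert set, and no Helmert order over three arms compares both EXER and COMB with control

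*SAP*

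**What the plan says.** The SAP's analysis text fits a mixed-effects model to the outcomes over the week-8 visit and three post-tests in three groups, "followed by the Helmert contrasts test (if any results are found to be significant"). It does not say which factor the contrasts act on, how the levels are ordered, what the coefficients are, which result triggers them, or at which visit they are judged. The only two-arm comparison named is EXER with COMB, in a separate model for attendance and home-exercise adherence.

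The protocol frames the question by programme:

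- **Aim:** to "investigate the effects of an individualized exercise programme with and without BCE strategies for community-dwelling frail older people".
- **Sample size section:** a biostatistician "will randomize the centres into either: control, EXER, or COMB", and the pilot "effect sizes for the EXER and COMB groups were 0.51 and 0.23, respectively; whereas the overall effect size was 0.21". The pilot changes run "from pre-test to immediately post-intervention in the pilot study".
- **Interventions section:** "Another 16-week programme with a combination of exercise and health talks will be arranged for the EXER group", while "participants in the control group will attend only the health talks with no other intervention". The talks match the BCE sessions in number and timing: "To control the group and social interaction effects of the BCE programme for the COMB group".

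**The concern.** A three-arm trial with a control group will be asked three things: does exercise alone beat control, does exercise with BCE beat control, and do the two programmes differ? Helmert contrasts on three levels provide two rows, so at least one of these has no named test. Which one is missing depends on an order the SAP does not give. If the order is chosen after the data are seen, so is the hypothesis. What is at stake is a pre-specified estimate and interval for each programme against control, and protection against choosing contrasts later. The data and the model are not at risk.

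**Working it through.** **1. What each order tests.** A Helmert set on three arms is one arm against the mean of the other two, then those two against each other. Comparing each level with later or with earlier levels does not change that structure. Pilot mean changes are control -0.58, EXER -5.16 and COMB -2.66 (protocol, sample size section).

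| Set apart (two orders each) | First row, pilot means | Only pair tested | Control pairs missing |
|---|---|---|---|
| Control | -0.58 - (-5.16 - 2.66)/2 = 3.33 | EXER v COMB | both |
| EXER | -5.16 - (-0.58 - 2.66)/2 = -3.54 | COMB v control | EXER v control |
| COMB | -2.66 - (-0.58 - 5.16)/2 = 0.21 | EXER v control | COMB v control |

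Four of the six orders contain one control pair and none contains both. (The 0.21 points here only coincidentally matches the overall effect size of 0.21.) If the factor is visit, the rows compare times and no arm contrast is named.

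**2. What the pilot effect sizes are.** EXER minus control is 5.16 - 0.58 = 4.58 points, and 4.58/0.51 = 8.98. COMB minus control is 2.66 - 0.58 = 2.08 points, and 2.08/0.23 = 9.04. Both imply an SD of about 9.01, so 0.51 and 0.23 are consistent with each arm against control. The root mean square deviation of the three means divided by 9.01 is 0.208, which reproduces the plan's 0.21 as Cohen's f. The 76 per group is taken as given. It does not reproduce with the stated ICC (ANOVA needs 74 without clustering and 90 with it), but this point does not depend on that.

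**3. Power at one visit, without a gate.** Inputs are 76 per arm, four centres per arm and ICC 0.01 (protocol); equal centres are assumed. Design effect = 1 + (19 - 1) x 0.01 = 1.18. SE of a pair in SD units = sqrt(2 x 1.18/76) = 0.176. SE of the pooled row = sqrt(1.5 x 1.18/76) = 0.153. Two-sided 0.05 t test on 3 x 76 - 3 = 225 df, with 12 - 3 = 9 centre-level df in brackets:

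- EXER v control: 0.51/0.176 = 2.89, power 82% (73%)
- COMB v control: 0.23/0.176 = 1.31, power 26% (22%)
- COMB v EXER: 2.50/9.01 = 0.277; 0.277/0.176 = 1.57, power 35% (29%)
- Control v mean of both: 3.33/9.01 = 0.37; 0.37/0.153 = 2.42, power 68% (58%)

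Control-first therefore leaves out the best-powered pair.

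**4. Error rate and the price of pairs.** Simulation with 1,000,000 draws per case: three arm means with variance 1.18/76 and an independent chi-square variance estimate.

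- No effect in any arm: at least one of three unadjusted pairs is significant in 12% (11%). If a significant 2-df three-arm F test is required first, the figure is 5.0% (5.0%). If centre clustering is left out of the standard errors, that F test itself rejects about 8%.
- Both programmes at 0.51: a control pair v the pooled row has power 82% v 91% (73% v 84%) ungated, and 78% v 85% (65% v 71%) with both gated.
- Pilot effects: the gate lowers EXER v control from 82% to 72% (73% to 57%).

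**5. Does the pooled row mislead about COMB?** Gated, control first. Under pilot effects the pooled row is significant without EXER v COMB in 38% (30%) of trials. COMB v control is not significant in 17 (14) of those percentage points; EXER v control is not significant in only about 0.4 (0.2). With COMB truly inert, the pooled row alone is significant in 6% (5%), and COMB v control is also not significant in about 5% (4%) of all trials.

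**The case against.** Control-first Helmert is a respectable choice. It asks whether an exercise programme beats talks alone and then whether BCE changes the result, which suits the matching of talks to BCE sessions. The SAP mentions the contrasts directly after the three groups, so arm is the likelier factor. The aim does not name control comparisons. The pooled row is the stronger test if both programmes work equally. It also mixes packages no more than COMB v control does, since that pair changes exercise and BCE together. The planned model can estimate every pair, and under pilot effects adding EXER v control would rarely change the conclusion about exercise.

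All of this stands, and it limits the point to unspecified contrasts and missing pairwise estimates. It does not supply the order or coefficients, and it does not give a reader each programme's effect against control.

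A reader might go further and infer that a significant pooled row would wrongly credit COMB. The documents do not support that. Under the pilot figures COMB has a true effect of 0.23, so taking the row as support for COMB is not false; the pair usually fails for lack of power. The reading is wrong only if COMB is inert, and then the pattern occurs in only about 5% (4%) of trials.

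**Conclusion.** The point holds as a specification gap of low severity. The absence of factor, order and coefficients, and the fact that no Helmert order contains both control comparisons, follow from the text and need no simulation. The order matters: 3.33 against 0.21 points in the first row with pilot means.

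The power figures rest on pilot effects, 76 per arm in equal centres, ICC 0.01, one visit and clustering carried in the standard errors. They illustrate size and do not describe the SAP's own trigger, which is not defined. That Helmert contrasts are wrong in themselves, or that the trial cannot estimate the pairs, does not follow.

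**What to change.** In the SAP, state that the contrasts are on the between-arm difference in change from T0 (arm x time), with order control, EXER, COMB, and write out:

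- EXER v control (-1, 1, 0)
- COMB v control (-1, 0, 1)
- COMB v EXER (0, -1, 1)

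Report all three estimates with 95% CIs whatever the omnibus result. Keep the pooled contrast (-1, 0.5, 0.5) as supportive.

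The sponsor should also state an error-rate rule for significance claims. One option is a 2-df three-arm test at one visit named in advance, then each pair at 0.05. This holds 5% only if centre clustering is in the model, and the SAP would then have to say how the 2-df test is combined over the multiple imputations. The rule and the visit are separate choices for the sponsor.

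The core change costs wording only. The downsides are more contrasts to report and, if both programmes work equally, less power for a pair than for the pooled row. A gate, if chosen, takes further power from EXER v control, as shown in the working.
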